8.4.2 Seizure diaries

Seizure diaries will be completed between T-4W to T0W and reviewed at randomisation (T0W). Post randomisation they will be reviewed, at weekly intervals for the first four weeks during home visits by the RP (T1W, T2W, T3W, T4W), at the final home visit (T11W) and at the clinic visit at week 12 (T12W). Seizure status will also be discussed during telephone review by the RP in weeks T5W to T10W. Information will be collected on the number of seizures, the type and whether the child was asleep or awake at the time of the seizure.

8.5 Substudies

8.5.1 Genetic Study

Whilst we know that melatonin secretion is highly heritable in humans (suggesting genetic reasons may be more important than environmental factors) no specific genetic cause had been identified. Mutations in ASMT, which encodes the last enzyme in the pathway that produces melatonin have now been described⁽³⁷⁾. Corresponding low levels of melatonin and sleep disorders are seen in the families where these mutations are found. The link is particularly strong in populations with learning difficulty and autism, where it has been speculated that additional mutations in neuroligins lead to an increased susceptibility to sleep disorders.

The ability to detect genetic variations that account for abnormal melatonin production has been described by the Human Genetics and Cognitive Functions laboratory at the Pasteur Institute, France, and some candidate genes have been identified. The first group of candidate genes are those encoding the enzyme synthesising melatonin (TPH2, AA-NAT, ASMT) and the receptors of the melatonin (MTNR1A, MTNR1B, GPR50). The second group are genes thought to play a role in the aetiology of both autistic spectrum disorders and learning difficulties, both of which markedly increase the risk of sleep disorders (NLGN, MAOA, MAOB, COMT, SLC6A4, GABAR).

We are working with the Pasteur Institute on a genome-wide association (GWA) study, the aim being to identify genetic variants, initially within the aforementioned candidate genes and then also across the remaining genomic regions, associated with abnormal melatonin production and subsequently with sleep disorder.

Single Nucleotide Polymorphisms (SNPs) across the genome will be genotyped using the patient's DNA from a simple saliva sample. Genotyping will be undertaken using Illumina's HumanCNV370-Duochip ('370k chip') by the Human Genetics and

Cognitive Functions team, who already have an impressive track record in this field and all the facilities for rapid, blinded, genotyping. The 370k chip captures 81% and 68% of HapMap genetic variants at $r^2 > 0.8$, in Caucasian and Asian populations respectively. It therefore provides high genomic coverage of the known human genome SNPs.

In order to make sense of genotype phenotype correlations, large populations, defined by as much objective data as possible, are required. The MENDS study is gathering objective actigraphic and salivary melatonin data on children who enter the study and the population we are studying is precisely the group where genetic mutations specific to melatonin production might be expected. The MENDS sub-study aims to address the following:

- (i) what is the nature of any association between sleep problems and melatonin levels?
- (ii) can we identify genetic markers associated with the severity of the sleep problem and/or melatonin level?
- (iii) can we identify genetic markers that are associated with an individual's ability to synthesise melatonin?
- (iv) can we identify genetic markers that are associated with an individual's response to melatonin treatment in sleep disorders?

This sub-study will therefore involve genotyping of all children initially recruited to the project with sleep disorders and developmental delay. As preliminary data suggests that autism may be particularly strongly associated with these genetic mutations, we will precisely define this subgroup using the Social Communication Questionnaire. If the questionnaire suggests the presence of autism in a child with no previous diagnosis a letter will be sent to the referring clinician highlighting this (Appendix J).

8.5.2 RECRUIT Study

It is proposed that MENDS will involve a qualitative substudy "Processes in recruitment to randomised controlled trials (RCTs) of medicines for children (RECRUIT)". RECRUIT was approved in its own right by the North West MREC at its meeting on 2 March 2007 (REF 07/MRE08/6).

RECRUIT will be examining communication processes in the recruitment of participants to MENDS with the aim of identifying strategies for subsequent trials of medicines for children to improve trial recruitment and conduct. RECRUIT will involve:

- a) Routine audio-recording of MENDS discussions (consultations) between families and practitioners (trial recruiters).
- b) Follow-up interviews with up to 8 families (parents and children where aged 7 or over) who agree to participate in MENDS.
- c) Follow-up interviews with up to 8 families (parents and children where aged 7 or over) who decline participation in MENDS.
- d) Follow-up interviews with up to 8 trial recruiters involved in approaching families to take part in MENDS.

Collection of data for a) will be facilitated by MENDS staff who will *routinely* seek permission to audio-record recruitment consultations from the families whom they approach for MENDS. Data for b, c and d will be collected by the Research Associates (RAs) employed on RECRUIT, who will be entirely independent of MENDS.

If permission for audio-recording is declined by a family the recruitment consultation will not be recorded. If permission is given the recruiter will activate an audio-recorder. At the end of the MENDS recruitment consultation the recruiter will discuss RECRUIT with the family and seek their permission to pass their details to one of the RAs employed on RECRUIT, who will then make contact with families and obtain written informed consent for participation in the RECRUIT study. Recordings from families who decline RECRUIT will be erased as soon as practicable. All families who express an interest in RECRUIT but are not selected for follow-up interview will be contacted by letter to thank them and inform them that their recordings have been erased. Audio-recordings of the recruitment consultations will only be released to the RECRUIT RAs after the consent of participants has been obtained.

All interviews for RECRUIT will be conducted by experienced RAs with proven skills in the conduct of research in sensitive settings. Any distress during the interviews will be managed with care and compassion by the RAs, and participants will be free to decline to answer any questions that they do not wish to answer or to stop the interviews at any point. The RAs will receive appropriate training and follow a clear protocol for managing participants whose level of distress gives cause for concern. Any such families will be supported in obtaining appropriate help. If necessary, and after discussion with the participant, the lead clinician responsible for the child's care will be informed.

To allow MENDS to become established and avoid the initial “teething” phase that most trials experience, sampling for RECRUIT will not begin until the trial has been recruiting for approximately 4 months. Sampling to RECRUIT (and therefore the routine audio-recording of trial consultations) will roll from trial site to trial site in blocks of up to 3 months' duration, with planned suspensions if accrual to RECRUIT allows. This will help to minimise the numbers of families who are approached but not selected for RECRUIT. Concentrating sampling at particular sites in time-limited blocks, with the possibility of planned suspensions, will minimise the impact of RECRUIT on MENDS and the risk of overburdening particular sites. It will also facilitate liaison with the sites and assist recruiters in routine audio-recording of consultations.

8.6 Other Assessments

8.6.2 Sleep Habits, Quality of Life and Cognitive Function

8.6.2.1 Children's Sleep Habits Questionnaire

A comprehensive, parent-report sleep screening instrument designed for school-aged children, the Children's Sleep Habits Questionnaire (CSHQ) yields both a total score and eight subscale scores, reflecting key sleep domains that encompass the major medical and behavioural sleep disorders in this age group. The questionnaire takes 10 minutes to complete and is carried out at T-4W and T0W. The RP will enter data from the CSHQ onto the corresponding eCRF and retain a photo-copy of the questionnaire at site. Original documents will be forwarded to the MCRN CTU.

8.6.2.2 PedsQL™ Family Impact Module

The PedsQL™ Family Impact Module takes approximately 5 minutes to complete and will be undertaken at T0W and T+12W. It is designed to measure the impact of paediatric chronic health conditions on parents and the family. It measures parent self-reported physical, emotional, social, and cognitive functioning, communication, and worry. The Module also measures parent-reported family daily activities and family relationships. The RP will enter data from the PedsQL™ Family Impact Module onto the corresponding eCRF and retain a copy of the questionnaire at site. Original documents will be forwarded to the MCRN CTU.

8.6.2.3 Epworth Sleepiness Scale

The Epworth Sleepiness Scale takes 2-3 minutes to complete and will be undertaken by the caregiver at T0W and T+12W. This is a simple, self-administered questionnaire, which provides a measurement of the caregiver's general level of daytime sleepiness. The RP will enter data from the Epworth Scale into the corresponding eCRF and retain a copy of the questionnaire at site. Original documents will be forwarded to the MCRN CTU.

8.6.2.4 Aberrant Behaviour Checklist (ABC)

The Aberrant Behaviour Checklist is completed at T0W and T+12W; taking 15 to 20 minutes, and is an instrument for assessing individual baseline behaviour and for evaluating behavioural change. The RP will enter data from the completed ABC onto the corresponding eCRF and retain a copy of the questionnaire at site. Original documents will be forwarded to the MCRN CTU.

8.6.2.5 Composite Sleep Disturbance Index (CSDI)

The Composite Sleep Disturbance Index is completed at T-4W, T0W and T+12W and takes 2 to 3 minutes to complete. This measure is based on allocating scores according to the frequency and severity of sleep problems.

Table 3: Scoring criteria for the components of the Composite Sleep Disturbance Score

Score	0	1	2
Frequency	<1 per week	1-2 times per week	3+ times per week
Duration	Few minutes	≤30 minutes	31 minutes +

Applying the scoring criteria of Table 3 the CSDI will be calculated as follows: Settling problems, night waking, early waking (before 5am) and co-sleeping will be measured in terms of weekly frequency and settling and nightwaking problems will also be assessed in terms of the nightly duration of the problem. Using the scores shown in Table 3 scores will range from 0 to 12.

8.6.3 Special Assays or Procedures

8.6.3.1 Salivary melatonin assay

Salivary melatonin levels will be measured on each patient at two time points in the study; at, T-1W (i.e. the evening prior to the randomisation clinic visit, T₀) and at T+10W (i.e. melatonin is not given on the evening of the telephone call and the salivary sampling is carried out the following evening). This should allow accurate categorisation of which children are physiologically phase delayed at the beginning of the study, which may prove to be an important variable when comparing responders to non-responders in a secondary analysis.

Methods

Saliva samples will be collected hourly from 5pm until bedtime on two separate occasions at:

- **T-1W**, on the night prior to the randomisation clinic visit
- **T+10W**, on the night AFTER a dose of trial treatment has been omitted and *on which night no trial medication should be given* (i.e. two doses will be missed at the beginning of the eleventh week of study treatment)

Salivary samples should be collected (instructions to participants Appendix D and researchers Appendix E) and stored by the parent in a domestic freezer at a maximum temperature of - 18°C and collected by the RP for storage until trial completion when they will be placed in dry ice and transported to the School of Biomedical and Molecular Sciences, University of Surrey, Guildford for blinded analysis.

Details of analysis

Assay protocols can be found in Appendix F. The time of dim light melatonin onset (DLMO) will be calculated using 2 x SD of the individuals baseline melatonin values.

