8.2 Schedule for Follow-up

(See also Table 2)

TIME (weeks)

Study Schedule

T-4W:

Clinic visit (Clinician and RP). In the outpatient department, potential participants will be screened by the clinician and RP and those identified as being eligible for entry into the study on the basis of meeting the inclusion and exclusion criteria will be invited to allow the trial RP to complete assessments and provide the sleep hygiene/behavioural information. Following fully informed written consent (by RP or investigator) they will be registered in the study and allocated a unique registration number. At this stage participants are consenting only to be registered and undergo the 4 week sleep hygiene intervention and assessments.

Adhering to a scripted dialogue (Appendix H), the RP will provide the family with a standardised booklet on basic sleep hygiene and behavioural intervention. No other intervention (behavioural, pharmacological or homeopathic) to try and improve their child's sleep will be initiated. They will be shown how to complete a 24-hour sleep diary and will be asked to maintain a continuous sleep diary record over the next 4 weeks. Additionally, for patients with a diagnosis of epilepsy a seizure diary will also be maintained. The RP will supply the actigraph to be applied for the next four weeks, explaining how it is worn and operated.

The following questionnaires and assessments will be carried out:

- Adaptive Behaviour Assessment System (ABAS)
- Children's Sleep Habits Questionnaire (CSHQ)
- Composite Sleep Disturbance Index (CSDI)

Arrangements will be made for the RP to visit them at home at T -2W (i.e. after 2 weeks of basic sleep hygiene and behavioural intervention)

T-2W:

Home visit 1 (study nurse). The RP will visit the home to discuss progress, although no additional sleep intervention advice will be provided. The actigraph will be downloaded, visually compared with the sleep diary and re-initialised. Reasons for major discrepancies with the sleep diary will be recorded.

For those who consent (separate consent process carried out at this visit), the following will be carried out:

- Collection of DNA sample (saliva sample)
- Completion of Social Communication Questionnaire

Equipment will be provided along with verbal and written explanations for undertaking the salivary melatonin collection, which will be carried out on the evening prior to the T0W clinic visit and at T+10W (see

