8.6.3.2 DNA analysis

After fully blinded genotyping has taken place, the results of the genotyping will be correlated with the salivary melatonin concentration, actigraphy results and clinical phenotype of the individuals. For the clinical phenotype outcomes, two approaches will be taken. Firstly, association with the primary outcome of the trial will be undertaken. Secondly, mutually exclusive subgroups will be defined (without reference to the genotyping results) with regard to a combination of the CSHQ, actigraphy and dim-light melatonin onset (DLMO) salivary sample results. The disorders most relevant to endogenous melatonin production will be Circadian rhythm sleep disorders (CRSD) either advanced, delayed or free-running.

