Appendix D: Instructions for Collection of Salivary Samples (for parents)

UniS

University
of Surrey

School of
Biomedical
and Molecular
Sciences

Instructions for Collection of Saliva Samples Version 2.0 Date 17/08/07

You should have been given

- 10 tubes, 5 packs of sponges and 1 pair of scissors – each tube should have your child's code and approximate times to take the sample and a space for you to fill in the exact time labelled on it
- labelled grip seal bags
- 2 saliva sample collection record sheets

Saliva samples should be collected on TWO different occasions –

1. The evening before your second clinic visit
2. The evening after the week 10 telephone call (your study nurse will remind you when she calls)

On both occasions we would like you to collect saliva samples approximately every hour from 5:00 pm to bedtime. Don't disturb your child and try to take more samples after you have snuggled them down in bed.

During this period we would ask you to ensure your child:

1. remains indoors and as quiet as possible (seated, lying down) in a dimly light room (e.g. a single table lamp on one side of the room, avoid being close to the window).
2. does not drink caffeinated drinks (e.g. coca cola, tea or coffee) from 1 pm (lunchtime) on the day of collection.
3. every hour collect a saliva sample into the appropriately labelled collection tube. The MENDS nurse will have chatted to you about the different ways of collecting the spit (saliva) and you should have also had a chance to practise this already.

First remove the cap from the plastic tube and then either:

a) Ask your child to spit into the tube. We need 2mls which is slightly less than half a teaspoon. This is the absolute minimum and more is even better.

OR

b) Place one of the saliva sponges in the child's mouth in the *cheek pouch* (the space between the gums and the inner cheek). Gently move the saliva sponge around the upper and lower cheek pouches on one side of the mouth to soak up as much saliva as possible. There is no need to 'scrape' the inner cheek with saliva sponges – simply collect as much saliva as possible from the cheek pouches. The sponge will absorb more saliva if it is left in the child's mouth for a longer time (up to 60 seconds). Once collected cut the sponge into the tube provided and seal the lid. Recycle/discard the plastic handle.

Repeat this process with a second sponge on the other side of the mouth.

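### Saliva sampling stops at bedtime, so melatonin onset is right-censored in the most delayed children, where late onset cannot be told from low production; the kit also falls short for bedtimes of 10 pm or later

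*Protocol*

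**What the plan says.** Section 8.6.3.1 sets the schedule: "Saliva samples will be collected hourly from 5pm until bedtime on two separate occasions". It gives the purpose as well: "This should allow accurate categorisation of which children are physiologically phase delayed at the beginning of the study". The time of dim light melatonin onset (DLMO) is to be derived from twice the standard deviation of the child's own baseline values.

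Appendix D repeats the window to parents, "On both occasions we would like you to collect saliva samples approximately every hour from 5:00 pm to bedtime", and adds "Don't disturb your child and try to take more samples after you have snuggled them down in bed". In context this tells parents to stop sampling once the child is settled. The kit listed there is "10 tubes, 5 packs of sponges and 1 pair of scissors", and it serves both evenings: "Saliva samples should be collected on TWO different occasions". Section 8.2 has the equipment handed over at the T-2W home visit for both collections.

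The results are used in two ways. Section 8.6.3.2 correlates genotype with salivary concentration, and it also forms subgroups from the CSHQ, actigraphy and DLMO together: "The disorders most relevant to endogenous melatonin production will be Circadian rhythm sleep disorders (CRSD) either advanced, delayed or free-running". Sections 4.2 and 9.3.2 list salivary concentration as secondary outcome 12 and variants linked to abnormal production as outcome 13. Section 8.5.1, question (iii), asks about the ability to synthesise melatonin.

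**The concern.** The trait of interest is a late onset, and the sampling window closes at a time set by the family's routine. Under section 5.1, criterion 4a, a child can enter because sleep comes more than an hour after the usual bedtime. Whether such a child's onset is observed depends on how late it is. Information is therefore lost because of the characteristic being classified, not at random.

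Two things are at stake. First, the statement in 8.6.3.1 about accurate categorisation fails for the children it most concerns. Second, a child sampled only before the rise shows low values all evening, as does a child who makes little melatonin. A variant that acts on timing could then appear associated with production, and a real production effect could be diluted by children who are merely late.

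**Working it through.** **Inputs.** Hourly sampling from 5 pm to bedtime on two evenings (8.6.3.1, Appendix D); 10 tubes in all (Appendix D); one entry route with sleep latency above 1 h, joined by and/or to a route with no latency condition (5.1, criteria 4a and 4b). The protocol does not give the children's bedtimes, the lead from onset to sleep, or the split of tubes between evenings. It states no figure for this assay's classification that could be reproduced.

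**Step 1: tubes.** Samples needed per evening = whole hours from 5 pm to bedtime + 1.

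| Bedtime | Per evening | Both evenings | Supplied |
|---|---|---|---|
| 7 pm | 3 | 6 | 10 |
| 8 pm | 4 | 8 | 10 |
| 9 pm | 5 | 10 | 10 |
| 10 pm | 6 | 12 | 10 |
| 11 pm | 7 | 14 | 10 |
| midnight | 8 | 16 | 10 |

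The kit suffices up to a 9 pm bedtime and, with samples on whole hours, fails from 10 pm however the tubes are divided. With an equal split (10/2 = 5) the last tube is at 9 pm, which leaves 1, 2 or 3 h unsampled before a bedtime of 10 pm, 11 pm or midnight.

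**Step 2: when onset is seen.** Write onset = bedtime + latency − lead, and last sample = bedtime − gap. Onset is observed only if latency ≤ lead − gap. For assumed leads of 1, 2 and 3 h:

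| Situation | Gap | Longest latency still observed |
|---|---|---|
| Whole-hour bedtime up to 9 pm | 0 h | 1, 2, 3 h |
| 8:30 pm bedtime, whole-hour samples | 0.5 h | 0.5, 1.5, 2.5 h |
| 10 pm bedtime, five tubes | 1 h | 0, 1, 2 h |

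For any lead, the longest latencies are lost first.

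**Step 3: how many.** Assume the lead varies with SD 0.5 h. If the last sample is taken at bedtime, the share with unseen onset is Φ((latency − lead)/0.5). If it is taken at the last whole hour at or before bedtime (bedtime SD 0.5 h), simulation of 200,000 children per setting gives the second result.

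| Latency | Lead | Sample at bedtime | Last whole hour |
|---|---|---|---|
| 2 h | 1 h | Φ(2) = 98% | about 100% |
| 2 h | 2 h | Φ(0) = 50% | 81% |
| 2 h | 3 h | Φ(−2) = 2% | 20% |
| 1 h | 1 h | Φ(0) = 50% | 80% |
| 1 h | 2 h | Φ(−2) = 2% | 19% |
| 1 h | 3 h | Φ(−4) = 0% | 0% |

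With a mean bedtime of 10:30 pm, five tubes and a 2 h latency, the shares are 100%, 98% and 76% for leads of 1, 2 and 3 h.

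**Step 4: late against low.** Take two children with an 8 pm bedtime and samples at 5, 6, 7 and 8 pm. One has a normal rise starting at 8:30 pm; the other has a weak rise at any hour. Both return only low values. No cut-off applied to those four samples separates them, because the information lies after the last tube.

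**The case against.** A reader might infer that the DLMO rule returns no value in phase-delayed children and so empties them out of the delayed group. The documents do not support that.

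- **The rule need not return nothing.** The protocol does not say which samples are baseline or whether a mean is added. If all five samples are baseline and the cut is mean + 2 SD, no child can cross, delayed or not: the largest possible value is (n − 1)/√n = 4/√5 = 1.79 SD. If only the first 2, 3 or 4 of five are baseline, a flat profile with normal noise crosses in 34%, 19% or 9% of evenings. With no mean added, a flat profile with a 20–40% coefficient of variation crosses in about 71% of evenings or more. A censored child may therefore get a false onset time. That does not help the accuracy claim, but it differs from a missing value.
- **Saliva is not the only classifier.** The subgroups in 8.6.3.2 also use the CSHQ and actigraphy, so a child without an onset time does not automatically leave the classification. A missing crossing also carries information, if it is recorded as later than the last sample.
- **The tube limit is secondary.** It binds only from about a 10 pm bedtime, and the equal split is inferred.
- **The percentages do not fix a size.** They rest on an undocumented lead and fall sharply if the last sample is taken at bedtime, which Appendix D allows. Some children enter on criterion 4b alone.
- **Analysis rules may sit in the SAP** (9.1, 9.6), so the absence of a censoring rule from the protocol is not itself an error.

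All of this stands. What remains is protocol content: the window, the kit and the accuracy claim. Leaving settled children undisturbed is a deliberate choice and is not disputed here. No analysis can recover an onset that was never sampled.

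**Conclusion.** The point holds in limited form. Onset is right-censored at the last sample, and the children censored are the most delayed, not phase-delayed children in general. For them 8.6.3.1 does not deliver accurate categorisation, and using evening concentration as a guide to production can take phase delay for low output. The bedtime stop is the main cause. The kit is a separate, smaller inconsistency: 10 tubes against at least 12 for a bedtime of 10 pm or later.

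The direction follows from the schedule alone. The size does not: it depends on bedtimes and on the lead from onset to sleep, neither of which the protocol gives. Secondary outcomes 12 and 13, the phase-delay comparison of responders with non-responders, and the genetic sub-study are affected. The primary outcome comes from the sleep diary and is untouched.

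**What to change.** 1. In 8.6.3.1 and 8.6.3.2, class a child with no threshold crossing as having an onset later than the clock time of the last sample, and analyse onset time as right-censored there, not as missing.
2. Keep all children in the concentration analysis. Flag those with no observed onset as late or low, not distinguishable, and add a sensitivity analysis without them. Restricting the main analysis to observed onsets would remove the genuine low producers whom the genetic sub-study seeks.
3. Supply enough tubes to reach each child's own bedtime on both evenings, and ask for a sample at bedtime. With that extra sample, any bedtime after 9 pm needs at least six tubes per evening, or 12 in all.
4. Reword the accuracy statement in 8.6.3.1 to say that an onset after bedtime is known only to be late.

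The cost is a few more tubes per kit and some protocol and analysis wording. Fewer children will carry an exact onset time. No sampling after the child has settled is needed.
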